APPENDIX I. SCHEDULE OF EVENTS32
APPENDIX II. SUBJECT INSTRUCTIONS FOR USE.....33
APPENDIX III. LOCAL SKIN RESPONSE.....37
APPENDIX IV. VAS PAIN ASSESSMENT.....38
APPENDIX V. SKINDEX-16.....39

LIST OF ABBREVIATIONS

AE	adverse event
AK	Actinic keratosis
ALT	alanine aminotransferase
AST	aspartate aminotransferase
BUN	blood urea nitrogen
CFR	Code of Federal Regulations
CRF	case report form
CRP	C-reactive protein
DMC	Data Monitoring Committee
DSMB	Data Safety Monitoring Board
FDA	Food and Drug Administration
GCP	Good Clinical Practice
HIPAA	Health Insurance Portability and Accountability Act of 1996
ICF	informed consent form
ICH	International Conference on Harmonisation
IEC	Independent Ethics Committee
IRB	Institutional Review Board
ITT	Intent-to-treat
LOCF	last observation carried forward
LSR	Local skin response
NSAID	nonsteroidal anti-inflammatory drug
OTR	organ transplant recipients
PI	Principal Investigator
PK	pharmacokinetic
SAE	serious adverse experience
SAP	Statistical Analysis Plan
SCC	squamous cell carcinoma
SGOT	serum glutamic oxaloacetic transaminase
SGPT	serum glutamate pyruvate transaminase

PROTOCOL SYNOPSIS

TITLE	Safety and efficacy of ingenol mebutate gel 0.015% for treatment of actinic keratosis on the face in solid organ transplant recipients
SPONSOR	Investigator Initiated Protocol
FUNDING ORGANIZATION	Leo Pharma
NUMBER OF SITES	1
RATIONALE	
Actinic keratoses (AK) are patches of dysplastic keratinocytes arising in sun-damaged skin. These lesions are precursors to cutaneous squamous cell carcinoma (SCC), and are treated to prevent progression to SCC. First-line therapy for AK include cryotherapy and curettage, which target clinically visible lesions but do not address the subclinical lesions in the field of ultraviolet radiation damage. Field therapy includes topical chemotherapy, immunotherapy, and photodynamic therapy. Ingenol mebutate is the active compound found in Euphorbia peplus sap, and has been approved for treatment of actinic keratoses in immunocompetent patients. Ingenol mebutate 0.015% is favored over other topical treatments for treatment of actinic keratoses on the face due to the brief treatment course, high clearance rate, and resolution without sequelae. There are no data on safety of this medication in immunosuppressed solid organ transplant recipients (OTR). OTR have a high incidence of AK and high risk of developing SCC, and require frequent field therapy. In addition, OTR generally have a higher burden of AK and require treatment of a larger surface area than the 25 cm² area labeled for ingenol mebutate 0.015%. We plan to investigate the safety and efficacy of ingenol mebutate 0.015% in OTR, with a treatment area up to 100cm².
 
The rationale for an increased dose and surface area for treatment in this study is that OTR typically have an extensive burden of AK, requiring treatment of larger areas such as those described here. The proposed treatment regimen better reflects the 'real world' need for treatment of a larger surface area while evaluating the safety and local site reactions associated with this treatment regimen.

STUDY DESIGN	This is a single arm, open-label safety study.
PRIMARY OBJECTIVE	To assess the safety of topical ingenol mebutate for treatment of the face in solid organ transplant recipients.

SECONDARY OBJECTIVES	
To evaluate the efficacy of ingenol mebutate for reduction of actinic keratoses on the face in organ transplant recipients.
 
To investigate the local skin response to ingenol mebutate in organ transplant recipients.
 
To investigate the effect of topical treatment with ingenol mebutate on patient reported outcomes of pain and quality of life in organ transplant recipients.

NUMBER OF SUBJECTS	20
SUBJECT SELECTION CRITERIA	
Inclusion Criteria:
 
 • Adults at least 18 years old. • Subject must be a solid organ transplant recipient at least one year from the date of transplantation. • Subjects must be in stable health as confirmed by medical history, per investigator judgement. • Subjects must be able to read, sign, and understand the informed consent. • Subjects have at least 4 and no more than 20 clinically typical, visible actinic keratoses in a treatment area of approximately 100cm² on the face. Treatment areas will include a single cheek (nasofacial sulcus to tragus, malar cheekbone to jawline and avoiding the lower eyelid and mouth); the forehead (hairline to eyebrows, extending laterally to the root of the helix). • Subject must be willing to forego any other treatments on the face, including cryotherapy, tanning bed use and excessive sun exposure while in the study. • Subject is willing and able to participate in the study and to comply with all study requirements including concomitant medication and other treatment restrictions. • If subject is a female of childbearing potential she must have a negative urine pregnancy test result prior to study treatment initiation and must agree to use an approved method of birth control while enrolled in the study. 
Exclusion Criteria:
 
 • Subjects with an unstable medical condition as deemed by the clinical investigator. • Subjects with a history of bone marrow or stem cell transplantation. • Subjects with non-melanoma skin cancer in the treatment area.

	
 • Subjects with any dermatologic disease in the treatment area that may be exacerbated by the treatment proposed or that might impair the evaluation of AKs. • Women who are pregnant, lactating, or planning to become pregnant during the study period. • Subjects who have previously been treated with ingenol mebutate in study area within the past 8 weeks. • Subjects who have used any topical prescription medications for actinic keratosis on the study area within 8 weeks prior to study treatment initiation. • Subjects who have used any topical prescription medications for other reason on the study area within 4 weeks prior to study treatment initiation. • Subjects who are currently participating in another clinical study or have completed another clinical study with an investigational drug or device on the study area within 30 days prior to study treatment initiation. • Subjects with known hypersensitivity to Picato gel or any of the inactive ingredients: isopropyl alcohol, hydroxyethyl cellulose, citric acid monohydrate, sodium citrate, or benzyl alcohol.

TEST PRODUCT, DOSE, AND ROUTE OF ADMINISTRATION
	
Ingenol Mebutate, 0.015% topical gel
 
Subjects will treat a 100 cm² area of the skin daily for 3 days based on the per label dosing for the 0.015% concentration, and assuming a deliverable dose weight of 0.25g. Therefore, 4 tubes of the 0.15% concentration will be used in the treatment area per day, for 3 consecutive treatment days, for a total of 12 tubes of the 0.015% concentration per patient. This will deliver a dose of 1.5 mcg per cm² of treated area each day. Subjects will be instructed to open one tube at a time and apply contents to one 25 cm² skin quadrant, and then repeat for each of the remaining three quadrants. The first application will be performed in clinic under the guidance of the study coordinator.

DURATION OF SUBJECT PARTICIPATION AND DURATION OF STUDY
	
Subjects will be on study for up to 57 days
 
Screening: up to 14 days
 
Treatment: 3 days
 
Follow-up: 54 days
 
The total duration of the study is expected to be 8 months. 6 months for subject recruitment and 2 months for final subject follow-up.

CONCOMMITANT MEDICATIONS	
Allowed: Bland topical emollients such as Eucerin, Cetaphil. 1% topical hydrocortisone cream or ointment allowed after D4 at the discretion of the investigator.
 
Prohibited: Any topical prescription medication on the treatment area during the study.

EVALUATIONS	
PRIMARY ENDPOINT	
The primary outcome will be the safety endpoint of the incidence rate of patients who experience:
 
 1) Any adverse event (AE) ascertained by patient report, physician evaluation, or laboratory value. 2) One or more serious adverse events (SAE) as defined by CTCAEv4 3) Adverse events leading to study drug discontinuation.
SECONDARY ENDPOINTS	
Efficacy:
 
 • Reduction in number of actinic keratoses: defined as the percent change in actinic keratosis count in the target treatment area on Day 57, as compared to the baseline lesion count. • Partial clearance of lesions: defined as the proportion of patients with a reduction of 75% or more in the number of clinically visible AKs in the target treatment area at Day 57, compared to baseline. • Complete clearance of lesions: defined as the proportion of patients with complete clearance of actinic keratoses in the target treatment area. 
Local skin response:
 
 • Local skin response (LSR) as measured by visual assessment by the investigator using a 4 point scale on six responses for a maximum total of 24, according to the LSR scoring scale. 
Patient Reported Outcomes:
 
 • Pain as measured by the 0-10 VAS Numeric Pain Distress Scale (0 = no pain, 5 = moderate pain, 10 = unbearable pain). • Patient quality of life as measured by Skindex-16 survey
STATISTICS Primary Analysis Plan	
This is a small descriptive study, with the primary safety endpoint of the incidence rate of patients who experience:
 
 1) Any adverse event (AE) ascertained by patient report, physician evaluation, or laboratory value, 2) One or more serious adverse events (SAE) as defined by CTCAEv4, and 3) Adverse events leading to study drug discontinuation. 
The safety analysis will be based on the safety population, which is defined as all randomized patients who have received at least one dose of study medication and who have had at least one post-baseline

	
safety evaluation.
 
Adverse events will be explored for trends or heterogeneity between the two transplant subgroups; lung and kidney. If there is evidence for a difference between groups, the subgroups will be reported separately.
 
The mean maximum LSR composite score, the VAS score, and the Skindex-16 scores and trend in scores over the study visits will be reported as descriptive data. The composite LSR score will be compared to historical controls (Lebwohl et al, NEJM 2012).
 
The efficacy analysis will be based on the intent-to-treat (ITT) population. In the ITT population, patients will be counted in the treatment group upon informed consent, regardless of receiving any dose of study medication.
 
For efficacy analysis, all missing values due to patient early termination from the study will be imputed using last observation carried forward (LOCF) method, as appropriate. For each patient, the Baseline values will be defined as those values recorded at Day 1 prior to dosing or Screening as appropriate. Patients who are lost-to-follow-up after Baseline will be included to the ITT population carrying forward their Baseline values, i.e., these patients will be considered as treatment failures.
 
Percent reduction in number of actinic keratoses and proportions of patients with partial and complete clearance of actinic keratoses will be presented descriptively and visualized as histograms. These scores will be compared to historical controls (Lebwohl et al, NEJM 2012).

Rationale for Number of Subjects
	
This is a pilot descriptive sample, not powered for analysis. The sample size of 20 patients is selected to achieve a reportable sample size in two subgroups of organ transplant recipients.

1 BACKGROUND

Ingenol mebutate is the active compound found in *Euphorbia peplus* sap, and has been approved for treatment of actinic keratoses in immunocompetent patients. Ingenol mebutate 0.015% is favored over other topical treatments for treatment of actinic keratoses on the face due to the brief treatment course, high clearance rate, and resolution without sequelae. There are no data on safety of this medication in immunosuppressed solid organ transplant recipients (OTR). OTR have a high incidence of AK and high risk of developing SCC, and require frequent field therapy.

2 STUDY RATIONALE

Actinic keratoses (AK) are precursors to cutaneous squamous cell carcinoma (SCC), and are treated to prevent progression to SCC. First-line therapy for AK include cryotherapy and curettage, which target clinically visible lesions but do not address the subclinical lesions in the field of ultraviolet radiation damage. Field therapy includes topical chemotherapy, immunotherapy, and photodynamic therapy. Ingenol mebutate is the active compound found in *Euphorbia peplus* sap, and has been approved for treatment of actinic keratoses in immunocompetent patients. Ingenol mebutate 0.015% is favored over other topical treatments for treatment of actinic keratoses on the face due to the brief treatment course, high clearance rate, and resolution without sequelae.

There are no data on safety of this medication in immunosuppressed solid organ transplant recipients (OTR). OTR have a high incidence of AK and high risk of developing SCC, and require frequent field therapy. In addition, OTR generally have a higher burden of AK and require treatment of a larger surface area than the 25 cm² area labeled for ingenol mebutate 0.015%. We plan to investigate the safety and efficacy of ingenol mebutate 0.015% in OTR, with a treatment area up to 100 cm².

The rationale for an increased dose and surface area for treatment in this study is that OTR typically have an extensive burden of AK, requiring treatment of larger areas such as those described here. The proposed treatment regimen better reflects the 'real world' need for treatment of a larger surface area while evaluating the safety and local site reactions associated with this treatment regimen.

2.1 Risk / Benefit Assessment

The risks of ingenol mebutate are primarily local site reactions of redness, flaking, crusting, swelling, blisters, or erosions. These typically begin at day 1 of treatment. The adverse reactions reported in $\geq 2\%$ of patients treated with ingenol mebutate were application site pain, pruritus, and infection; periorbital edema, and headache. We will monitor the patients at day 4 and counsel them on mitigating site reactions with gentle skin care, cold packs, pain control if needed. Patients will also be counseled to carefully avoid the eye and lip area. We expect the infection rate in OTR to be less than the reported

rate of 3% as the majority of OTR are on routine antibiotic prophylaxis; any infections will be recorded as adverse events and treated according to standard of care.

If a patient has a (1) local skin response score of 3 or greater in any individual category, and (2) associated symptoms unrelieved by supportive care such as ice packs and nonsteroidal anti-inflammatory drug (NSAID), then 1% topical hydrocortisone cream or ointment is allowed after Day 4 at the discretion of the investigator.

Ingenol mebutate has accepted benefits for AK which outweigh the risks. OTR have a high burden of AK and frequently require multiple rounds of field treatment to reduce this sign of ultraviolet radiation induced skin damage. Other treatments require long-term applications or in-office light; ingenol has the benefit of being a short course. Ingenol mebutate is approved for immunocompetent patients, but there is no safety data in OTR. Despite this, the medication has been frequently used off-label in OTR and is generally believed to be safe due to the absence of systemic absorption. One recent case reported brisk local site reaction without systemic adverse events.

It is difficult to obtain insurance coverage for ingenol mebutate in OTR without demonstrating failure of multiple other treatments for AK. Participants in this study will also benefit from access to ingenol mebutate.

3 STUDY OBJECTIVES

3.1 Primary Objective

The primary objective is to assess the safety of topical ingenol mebutate 0.015 % for treatment of the face in solid organ transplant recipients.

3.2 Secondary Objectives

The secondary objectives are (1) to evaluate the efficacy of ingenol mebutate for reduction of actinic keratoses on the face in organ transplant recipients; (2) to investigate the local skin response to ingenol mebutate in organ transplant recipients; (3) to investigate the effect of topical treatment with ingenol mebutate on patient reported outcomes of pain and quality of life in organ transplant recipients.

4 STUDY DESIGN

4.1 Study Overview

This is a single arm, open-label interventional study of ingenol mebutate 0.015% in solid organ transplant recipients. Twenty subjects are planned; 10 kidney transplant recipients and 10 lung transplant recipients. These populations have been selected as they represent the spectrum of solid organ transplantation: kidney transplant recipients are the largest transplant population, but have lower levels of immunosuppression and skin cancer risk. Lung transplant recipients have the highest burden of skin cancer and actinic keratoses.

Screening data will be reviewed to determine subject eligibility. Subjects who meet all inclusion criteria and none of the exclusion criteria will be enrolled into the study.

The following treatment regimens will be used:

- Experimental treatment: Ingenol mebutate 0.015%, topical gel
- Placebo or Comparator: None

Total duration of subject participation will be 57 days. Total duration of the study is expected to be 8 months.

5 CRITERIA FOR EVALUATION

5.1 Primary Efficacy Endpoint

The primary efficacy endpoint will be the safety endpoint of the incidence rate of patients who experience (1) any adverse event ascertained by patient report, physician evaluation, or laboratory value; (2) one or more serious adverse events as defined by CTCAEv4; (3) adverse events leading to study drug discontinuation.

The primary efficacy endpoint will be assessed from screening to Day 57 or study completion.

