5.2 Secondary Efficacy Endpoints

The secondary efficacy endpoints are efficacy, local skin response, and patient reported outcomes. These endpoints will be assessed from screening to Day 57 or study completion.

Efficacy:

- Reduction in number of actinic keratoses: defined as the percent change in actinic keratosis count in the target treatment area on Day 57, as compared to the baseline lesion count.
- Partial clearance of lesions: defined as the proportion of patients with a reduction of 75% or more in the number of clinically visible AKs in the target treatment area at Day 57, compared to baseline.
- Complete clearance of lesions: defined as the proportion of patients with complete clearance of actinic keratoses in the target treatment area.

Local skin response:

Local skin response (LSR) as measured by visual assessment by the investigator using a 4 point scale on six responses for a maximum total of 24, according to the LSR scoring scale.

Patient Reported Outcomes:

- Pain as measured by the 0-10 VAS Numeric Pain Distress Scale (0 = no pain, 5 = moderate pain, 10 = unbearable pain).
- Patient quality of life as measured by Skindex-16 survey

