10 EVALUATIONS BY VISIT

The following is a list of evaluations scheduled to occur at each visit. Screening and Visit 2 visits can occur on the same day.

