10.2 Visit 2 (Day 1)

1. Record any Adverse Events.
2. Concomitant medications review.
3. Perform a complete physical examination.
4. Perform an actinic keratosis count.
5. Perform a local skin response assessment.
6. Subject to perform a VAS pain assessment.
7. Subject to complete the Skindex-16.
8. Perform photography in treatment area.
9. Collect urine sample and perform urine pregnancy test (if applicable).
10. Dispense a kit of ingenol mebutate 0.015% gel; subject will complete the first application under the investigator's supervision in the clinic.
11. Dispense subject 2 additional kits for use on Day 2 and Day 3. Subject will also be provided with a detailed application instructions hand-out.
12. Schedule subject for Visit 3/ Day 4.

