11 ADVERSE EXPERIENCE REPORTING AND DOCUMENTATION

11.1 Adverse Events

An adverse event (AE) is any untoward medical occurrence in a clinical investigation of a patient administered a pharmaceutical product and that does not necessarily have a causal relationship with the treatment. An AE is therefore any unfavorable and unintended sign (including an abnormal laboratory finding), symptom or disease temporally associated with the administration of an investigational product, whether or not related to that investigational product. An unexpected AE is one of a type not identified in nature, severity, or frequency in the current U.S. package insert or of greater severity or frequency than expected based on the information in the U.S. package insert.

The Investigator will probe, via discussion with the subject, for the occurrence of AEs during each subject visit and record the information in the site's source documents. Adverse events will be recorded in the patient CRF. Adverse events will be described by duration (start and stop dates and times), severity, outcome, treatment and relation to study drug, or if unrelated, the cause.

AE Severity

The National Cancer Institute's Common Terminology Criteria for Adverse Events (CTCAE) Version 3.0 should be used to assess and grade AE severity, including laboratory abnormalities judged to be clinically significant. The modified criteria can be found in the study manual. If the experience is not covered in the modified criteria, the guidelines shown in Table 1 below should be used to grade severity. It should be pointed out that the term "severe" is a measure of intensity and that a severe AE is not necessarily serious.

Table 1. AE Severity Grading

Severity (Toxicity Grade)	Description
Mild (1)	Transient or mild discomfort; no limitation in activity; no medical intervention or therapy required. The subject may be aware of the sign or symptom but tolerates it reasonably well.
Moderate (2)	Mild to moderate limitation in activity, no or minimal medical intervention/therapy required.
Severe (3)	Marked limitation in activity, medical intervention/therapy required, hospitalizations possible.
Life-threatening (4)	The subject is at risk of death due to the adverse experience as it

	occurred. This does not refer to an experience that hypothetically might have caused death if it were more severe.
--	--

AE Relationship to Study Drug

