11.2.1 Serious Adverse Experience Reporting

The study site will document all SAEs that occur (whether or not related to study drug) per [UCSF CHR Guidelines](#). The collection period for all SAEs will begin after informed consent is obtained and end after procedures for the final study visit have been completed.

In accordance with the standard operating procedures and policies of the local Institutional Review Board (IRB)/Independent Ethics Committee (IEC), the site investigator will report SAEs to the IRB/IEC.

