15.1 Data Sets Analyzed

All eligible patients who are enrolled in the study and receive at least one dose of the study drug (the Safety Population) and who have had at least one post-baseline safety evaluation will be included in the safety analysis.

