15.3 Analysis of Primary Endpoint

This is a small descriptive study, with the primary safety endpoint of the incidence rate of patients who experience:

1) Any adverse event (AE) ascertained by patient report, physician evaluation, or laboratory value, 2) One or more serious adverse events (SAE) as defined by CTCAEv4, and 3) Adverse events leading to study drug discontinuation.

Adverse events will be explored for trends or heterogeneity between the two transplant subgroups; thoracic and abdominal. If there is evidence for a difference between groups, the subgroups will be reported separately.

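### The primary safety incidence is counted from screening with no first-application onset rule, and the Day 57 laboratory draw in 5.3 is missing from 9.2, 10.6 and Appendix 1

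*Combined protocol and SAP*

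**What the plan says.** **Start of the window.**

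- Section 5.1 sets the period for the primary endpoint: "The primary efficacy endpoint will be assessed from screening to Day 57 or study completion". The endpoint has three components: any AE found by patient report, physician evaluation or laboratory value; one or more SAEs; and AEs leading to discontinuation of study drug.
- Events are collected before dosing. Appendix 1 marks Adverse Events in the Screening column. At Visit 2 (Section 10.2), AEs are recorded at step 1, and the first application comes at step 10: "Dispense a kit of ingenol mebutate 0.015% gel; subject will complete the first application under" supervision. Section 11.2.1 states: "The collection period for all SAEs will begin after informed consent is obtained".
- Section 15.1 restricts the analysis to patients who "receive at least one dose of the study drug (the Safety Population") and have a post-baseline safety evaluation. This selects patients; it does not select events by onset.
- Section 15.3 repeats the components, for example "One or more serious adverse events (SAE) as defined by CTCAEv4", without an onset condition. The synopsis has none either.
- Section 11.1 describes an AE as "temporally associated with the administration of an investigational product", but gives no start point.

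**End of the window.** Section 5.3 schedules laboratory sampling at Screening, Day 4, Day 29, Day 57 and early termination. Section 9.2 and both laboratory rows of Appendix 1 give the same list without Day 57. The seven steps of Visit 6 in Section 10.6 include no blood collection.

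**The concern.** The incidence in 5.1 is the trial's primary result. There is no comparator, so nothing in the data shows how many events these transplant recipients would have had without the gel. An event that starts before the first application cannot be an effect of the gel, yet the stated window admits it if the patient is dosed later. An analyst who follows 5.1 and one who follows the definition in 11.1 could therefore report different counts. Component 3 is not affected, because it requires study drug to be stopped.

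The laboratory mismatch reaches the same endpoint at its other end. Component 1 includes AEs found by laboratory value and its window runs to Day 57, but three of the four places that set the schedule provide no blood sample at Day 57.

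**Working it through.** The plan gives no event rate, precision target or power to reproduce. Its stated size is 20 patients, 10 kidney plus 10 lung (4.1). The check is a comparison of texts plus simple arithmetic.

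**1. Can a pre-dose event be counted?**

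| Question | Where | Answer |
|---|---|---|
| When does the endpoint window open? | 5.1 | Screening |
| Are events recorded before the first application? | Appendix 1; 10.2 step 1; 11.2.1 | Yes |
| Must the patient be dosed? | 15.1 | Yes |
| Must the event follow the dose? | Synopsis, 5.1, 15.1, 15.3 | Not stated |
| Does any definition imply it? | 11.1 | Suggested, with no start point |

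So a pre-dose event in a patient who is later dosed can enter components 1 and 2.

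**2. How long is the pre-dose period?** Screening lasts S days, from 0 (Section 10: "Screening and Visit 2 visits can occur on the same day") to 14 (synopsis). Follow-up after Day 1 is 57 − 1 = 56 days. The pre-dose share of the window is S/(S + 56):

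- S = 14: 14/70 = 20.0%
- S = 7: 7/63 = 11.1%
- S = 0: 0%

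This is a share of time, not of events.

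**3. What does one patient change?** One patient is 1/20 = 5 percentage points overall, or 1/10 = 10 points in an organ subgroup. Exact (Clopper-Pearson) 95% limits:

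| Count | Limits | With one more patient | Limits |
|---|---|---|---|
| 0/20 | upper 16.8% | 1/20 | upper 24.9% |
| 10/20 | 27.2% to 72.8% | 11/20 | 31.5% to 76.9% |
| 0/10 | upper 30.8% | 1/10 | upper 44.5% |

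A patient changes category only if there is a pre-dose event and no qualifying event from first application to Day 57.

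**4. Illustration under assumed rates.** The documents give no background rate. Assume a constant 30-day probability q of a background AE, from 5% to 30%, full 14-day screening and 57 days on study. The probability of at least one event in w days is 1 − (1 − q)^(w/30).

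- q = 5%: 9.3% over 57 days and 11.4% over 71 days, a difference of 2.1 points, or about 0.4 of 20 patients.
- q = 30%: 49.2% and 57.0%, a difference of 7.8 points, or about 1.6 of 20 patients.

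These are background events only. Any treatment reactions recorded as AEs would shrink the difference for component 1, and same-day screening brings it to about zero.

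**5. Laboratory gap if 9.2, 10.6 and Appendix 1 are followed.**

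- Last scheduled draw to Day 57: 57 − 29 = 28 days; 28/56 = 50% of the time after Day 1.
- Section 9.2 accepts a chart value within 5 days of Day 29. From Day 24 the gap is 57 − 24 = 33 days; 33/56 = 59%.
- Section 9.2 also accepts a chart value within 14 days of Screening, and no draw is scheduled on Day 1. The last pre-dose value can therefore be 14 + 14 = 28 days old at first application.

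These gaps do not measure missed AEs.

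**The case against.** The strongest reply is that Section 11 already settles the matter. Section 11.1 ties an AE to administration of a product, and 11.2 defines an SAE as an AE that occurs at any dose, so an event before the first application is arguably neither. The 5.1 sentence may also be a standard description of a collection span: 5.2 says "These endpoints will be assessed from screening to Day 57 or study completion", although local skin response, VAS pain and Skindex-16 start only on Day 1. Section 10.1 has no AE step at Screening. Section 15 promises a detailed SAP before final analysis, and 9.1.10 records start dates and times, so either numerator can be derived later. In a descriptive study of 20 with no test or threshold, little may change.

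Much of this stands. The sentence may well have been meant as a collection span, the effect is probably small, and the SAP could hold the counting rule. It does not remove the defect. Neither definition names a start point, 11.2.1 itself collects SAEs from consent, and for AEs the 5.1 window matches what Appendix 1 collects.

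On laboratory sampling, it is fair that laboratory value is only one of three sources of AEs and that three of four places agree. The contradiction remains, and a later SAP cannot supply samples that were never drawn.

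**Conclusion.** The concern holds on both parts. As written, the primary incidence can include pre-dose events of dosed patients in components 1 and 2, and the plan has no rule to exclude them. The size depends on the length of screening (0% to 20% of the window) and on background rates that the documents do not give. It is probably small, but each patient affected moves the result by 5 or 10 points. This rests on reading 5.1 literally; reading it with 11.1 gives a different count, and that ambiguity is the problem.

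The Day 57 laboratory discrepancy is a direct contradiction and needs no assumption. If 9.2, 10.6 and Appendix 1 are followed, assessment of laboratory-detected AEs through Day 57 is not supported for completers.

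**What to change.** 1. In the synopsis, 5.1 and 15.3, count AEs and SAEs (components 1 and 2) with onset, or worsening of a pre-existing finding, from the first application through Day 57.
2. For laboratory findings, name the last pre-dose value as the reference (the Screening value, or the chart value that 9.2 allows) and record its date.
3. List events between consent and first application separately.
4. Reconcile 5.3 with 9.2, 10.6 and Appendix 1 on Day 57 sampling, and state the period over which laboratory-detected AEs are assessed.
5. Align 10.1 with Appendix 1 on recording AEs at Screening.

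The cost is wording in the protocol, carried into the SAP still to be written. The onset rule needs no new data, because 9.1.10 already captures start dates and times. The laboratory reconciliation adds a draw only if the Day 57 sampling in 5.3 is kept.
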